4.0 Test Schedule

Assessments, tests and procedures	Treatment			Observation ⁷
	Baseline ²	Last day of treatment (+/- 2 days)	12 weeks (+/- 8 weeks) post-radiation	12 months (+/- 3 month) post completion of radiotherapy, 24 months (+/- 3 months), 36 months (+/- 3 months), and at 5 years (+/- 3 months)
History and Physical exam (including breast assessment/exam) ¹	X	X	X	X
Mammogram	X ¹⁰			X ¹¹
Cosmesis ,QOL Outcome Assessment and Breast-Q ¹⁶ (see section 11.3 and Appendix)	X ¹³	X	X	X
Digital Photograph	X	X	X	X
Review of surgical specimen(s) to confirm eligibility	X ³			
Echocardiography ^{9, 14}	X ¹³			X ⁸
Radiation toxicity assessment (see section 10.4)	X	X	X	X
Serum pregnancy test	X ⁴			
Blood specimen ^{5, 17, R}	X ¹⁵	X	X	X ¹²
Surgical tumor specimen ^{6, 18, R}	X			

1. A general history & physical must be done \leq 8 weeks prior to registration. This should include an assessment of ECOG performance status (see Appendix I).

2. Following definitive surgical resection and adjuvant chemotherapy if indicated, prior to the start of radiation.
3. Outside pathology must be reviewed at the treating institution.
4. For women of childbearing potential only, must be within 7 days of radiotherapy
5. See section 14 for collection time and preparation of samples
6. See section 17 for collection time and preparation of samples
7. Patients that cannot come back to Mayo Rochester within the time constraints of the follow-up schedule; efforts to obtain outside records and send QOL's to be completed will occur, however the required items may not be captured.
8. Ideally 6-12 months post radiotherapy in HER2 positive patients treated with HER2 directed therapy and in patients treated with anthracycline as part of routine clinical care. Only followed for Echos 1 year post therapy.
9. Co-enrollment on IRB 15-007443 (echo protocol) is required in Rochester while open
10. Completed \leq 12 months prior to study entry
11. As clinically indicated
12. At 12 months post-treatment visit only to coincide with echocardiography.
13. Should be \geq 14 days since last chemotherapy
14. After closure of IRB 15-007443 (echo protocol) echocardiography tests will be performed only in left sided patients previously treated with anthracycline and/or HER2 directed systemic therapy. This correlative component will occur at Rochester Mayo only.
15. Baseline blood collection will be drawn through co-enrollment on IRB 15-000136 (Radiation Oncology Outcomes Registry and Biobanking Study).

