16. Breast-Q forms to be completed by patient at Observation timepoints.
17. Post radiation blood specimen submission for Rochester site only.
18. Surgical tumor specimen for Rochester site only.

R. Research funded

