16.62 Secondary Analyses

16.621 *Acute adverse events (up to 90 days post-RT):* All patients who were registered to the study and started treatment will be included in the acute adverse event analysis. An acute adverse event is an AE, regardless of attribution, that occurs up to 90 days post-RT. The maximum grade for each type of acute AE will be recorded for each patient. Data will be summarized as frequencies and relative frequencies by treatment arm. Additionally, the relationship of the adverse event(s) to the study treatment will be taken into consideration.

16.622 *Late adverse events and reconstruction failure:* All patients who were registered to the study and started treatment will be included in the late adverse event and reconstruction failure analysis. A late adverse event is an AE, regardless of attribution, that occurs at least 90 days post-RT and up to 5 years post-RT. The maximum grade for each type of late AE will be recorded for each patient. Data will be summarized as frequencies and

relative frequencies by treatment arm. Additionally, the relationship of the adverse event(s) to the study treatment will be taken into consideration.

- 16.623 *Quality of life*: The subscales of the BCTOS, elements from CTCAE-PRO, and other patient reported measures such as fatigue, breast pain, breast shape, and arm related morbidity outlined in the appendix will be summarized as the mean \pm SD and median (minimum value, maximum value). Changes in the QOL measurements from baseline will be determined at each follow-up visit and measured by treatment arm. The comparison of the changes at each time point between the two treatment arms within each cohort will be done with a paired t-test or Wilcoxon signed rank test, whichever is appropriate.
- 16.624 *Cosmesis*: The values of the cosmesis instruments (patient self-reported and panel-assessed) will be summarized with the frequencies and confidence intervals of fair or poor cosmesis events at baseline, 2 years, and 5 years by treatment arm.
- 16.625 *IBTR incidence*: The IBTR cumulative incidence will be estimated using a competing risks method (Gooley et al.) by treatment arm. The competing risks will be regional/distant breast cancer recurrence and death.

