18.0 Records and Data Collection Procedures

18.1 Submission Timetable

Initial Material(s) -

CRF	Treatment (Compliance with Test Schedule Section 4.0)
Institutional Contacts	
Patient Eligibility	
Demographics	
On-Study	≤2 weeks after registration
On Study: Neoadjuvant Chemotherapy	
Surgery	
Pathology of Ipsilateral Breast	
Breast Reconstruction	
Adjuvant Therapy	
Adverse Events- Baseline	
Specimen Submission: Blood (Baseline)	
Specimen Submission: Tissue (Baseline)*	*6 months after accrual

CRF	Treatment (Compliance with Test Schedule Section 4.0)
Patient Status: Baseline	
Patient Assessment	
Off Treatment	Submit ≤2 weeks after registration if withdrawal/refusal occurs prior to beginning protocol therapy

Test Schedule Material(s)

CRF	End of Treatment	12 weeks post/Observation Phase ⁴	Event Monitoring ⁵
Radiation Therapy	X		
Post Mastectomy Therapy: Chest Wall	X		
Radiation Therapy: Regional Nodes	X		
Patient Assessment	X	X	
Specimen Submission: Blood (post rad tx)	X		
Adverse Events Solicited	X	X	
Adverse Events: Other	X ²	X ²	
Off Treatment	X ²	X ²	
Patient Status Form	X	X	X
Specimen Submission: Tissue (Recurrence)		X ²	
Consent Withdrawal	X ²	X ²	
Lost to Follow-up	X ²	X ²	
Breast/Chest Wall Radiotherapy Questionnaire ³	X	X	

1. Complete at each evaluation during Active Treatment (see Section 4.0).
2. When applicable
3. Survey will need to be entered manually if has not alternately been scanned or entered electronically
4. Active monitoring observation phase, post radiation (+/- 2 days), 12 weeks (+/- 4 weeks), 12 months (+/- 30 days), annually for 4 years (+/- 3 months, total 5 years follow-up). If patient progresses within observation, they will move to the event monitoring phase where they will be followed until 5 years of follow-up information has been completed from the end of treatment timepoint
5. If patient has a recurrence prior to being off radiation therapy for 5 years, continue to follow yearly.

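### On its natural reading, footnote 16 of the test schedule leaves Breast-Q without a pre-radiotherapy value, and section 16 does not say how Breast-Q is to be analysed

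*Combined protocol and SAP*

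**What the plan says.** In section 4.0 one row, "Cosmesis ,QOL Outcome Assessment and Breast-Q", carries a mark at baseline, on the last day of treatment, at 12 weeks and in the Observation column. Footnote 16 is attached to Breast-Q alone and says: "Breast-Q forms to be completed by patient at Observation timepoints". The Observation column begins at 12 months and continues "post completion of radiotherapy, 24 months (+/- 3 months), 36 months (+/- 3 months), and at 5 years (+/- 3 months"). Footnote 2 defines baseline as "Following definitive surgical resection and adjuvant chemotherapy if indicated, prior to the start of radiation".

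Section 16.623 analyses the BCTOS subscales, CTCAE-PRO elements and other patient-reported measures "such as fatigue, breast pain, breast shape, and arm related morbidity outlined in the appendix". It then states: "Changes in the QOL measurements from baseline will be determined at each follow-up visit and measured by treatment arm". Section 16.2 also sends the reader to the appendix for measures of fatigue, pain and arm function. The appendices hold ECOG status, a cosmesis sheet scored by a nurse, and the reconstruction and mastectomy modules of the Breast-Q, both post-operative versions.

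**The concern.** The row and its footnote point in different directions, and a site has to choose between them. If it follows the footnote, the first Breast-Q is filled in a year after radiotherapy. The analysis section appears to need a baseline for measures in the appendix, and Breast-Q is the only patient-reported form there.

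Breast-Q is also the instrument that asks about the reconstructed breast and the chest area in most detail, and patient-reported outcomes are a secondary goal (section 2.2). With 72 evaluable patients, about 36 per arm, precision is scarce. A pre-radiotherapy score that is not collected before the first fraction cannot be recovered afterwards.

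**Working it through.** **Timing.** The plan uses the word observation in two places.

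- Section 4.0: four timepoints (12, 24, 36 months, 5 years), all after radiotherapy.
- Section 18.1, footnote 4, is wider: "Active monitoring observation phase, post radiation (+/- 2 days), 12 weeks (+/- 4 weeks), 12 months (+/- 30 days"), then annually. Even this starts after radiation.

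Neither includes baseline. The baseline mark in the shared row is explained by the cosmesis and QOL assessments, and a footnote on Breast-Q alone has little purpose unless it limits timing. Count under footnote 16, using section 4.0: four Breast-Q timepoints after radiotherapy, none before.

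**Link to the analysis.** Sections 11.3 and 11.4 and section 16 do not name Breast-Q. The link runs only through the word appendix in 16.2 and 16.623. Of four appendices, two are patient-reported, and both are Breast-Q. The content fits in part:

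- Pain in the breast area and difficulty moving the arm: in both modules.
- Breast shape: in the reconstruction module, not in the mastectomy module.
- Fatigue: in neither.

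**Whether a baseline is feasible.** Baseline follows mastectomy, so a post-operative form can be answered. The 16 physical-symptom items are the same in both modules, as are the 10 psychosocial items (the lead-in phrase to the latter differs slightly). These can be answered with an expander in place and by every patient. Module-specific scales would split each arm: at the plan's estimate of 2/3 reconstructed, 36 × 2/3 = 24 and 36 − 24 = 12.

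**Size.** The documents give no figure to reproduce. Let r be the correlation between baseline and follow-up score, an assumption here, with equal variance at both times. Relative to comparing follow-up scores alone, the variance of the arm difference is multiplied by

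- 1 − r² with the baseline as covariate;
- 2(1 − r) with change scores.

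For illustration, with 36 per arm all responding, two-sided 0.05 and 80% power, the detectable difference from follow-up scores alone is (1.960 + 0.842) × √(2/36) = 2.802 × 0.2357 = 0.66 SD. Multiply by the square root of each factor:

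| r (assumed) | Covariate factor | Detectable | Change-score factor | Detectable |
|---|---|---|---|---|
| 0.4 | 0.84 | 0.61 SD | 1.20 | 0.72 SD |
| 0.5 | 0.75 | 0.57 SD | 1.00 | 0.66 SD |
| 0.7 | 0.51 | 0.47 SD | 0.60 | 0.51 SD |

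Covariate adjustment cuts the variance by 16% to 49%. Change scores, the form in 16.623, raise it by 20% at r = 0.4, leave it unchanged at 0.5 and cut it by 40% at 0.7.

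**The case against.** The strongest reply is that the plan never assigns a change-from-baseline analysis to Breast-Q. Section 16.623 mentions fatigue, which Breast-Q does not measure. Section 11.4 speaks separately of other patient-reported questions, and section 18.1 lists a Breast/Chest Wall Radiotherapy Questionnaire that is not appended. The appendix pointer may mean that form. This stands, so a reader should not infer that a planned Breast-Q analysis has been made impossible for every patient. The alternative is no better, though: Breast-Q would then be collected four times with no stated analysis.

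A second reply is that footnote 16 does not say the observation visits are the only ones, and the row does mark baseline. That is fair, but it leaves two instructions to reconcile, and sites could differ.

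A reader might also infer that follow-up scores confound the surgical result with the radiotherapy effect. Between arms they do not: patients are randomised with balancing on immediate reconstruction (section 5.1), so a follow-up-only comparison is unbiased. Within an arm, the two cannot be told apart. Footnote 7 accepts that items may be missing for patients who cannot return, and without a baseline nobody can check whether responders in the two arms started from similar scores.

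Finally, some reconstruction-module items ask about the finished result, such as softness or whether the outcome met expectations. They suit a patient with an expander poorly, and her later change would include further surgery. That stands, and it is why the baseline should be confined, at the least, to the common scales.

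The registry described in section 11.4 might supply a baseline, but the documents do not say so for Breast-Q.

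**Conclusion.** The point holds as a minor one. On the natural reading of footnote 16 no pre-radiotherapy Breast-Q is collected, although the row marks baseline. Depending on what the appendix in 16.623 means, either a planned change from baseline cannot be computed for Breast-Q, or the instrument has no stated analysis. The documents do not settle which.

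The loss is one of precision, within-patient description and a check on responders, not of validity. Its size, a 16% to 49% cut in variance forgone, rests on an assumed correlation of 0.4 to 0.7 and applies to covariate adjustment only. It should not be credited to the change scores that 16.623 describes. BCTOS and the other QOL assessments keep their baseline, and the primary endpoint is untouched.

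**What to change.** - **Footnote 16:** state that Breast-Q is completed at baseline, before the first fraction, as well as at the observation timepoints. At the least, collect the physical-symptom and psychosocial scales at baseline.
- **Section 16.623:** name Breast-Q and the scales analysed, and compare the arms at 24 months by a model for the follow-up score with the baseline score as covariate, not by change score. Say which form holds the fatigue measure.
- **Patients enrolled without a baseline:** report post-treatment scores only.
- **If the sponsor prefers follow-up only:** say so in footnote 16 and 16.623, and remove the baseline mark for Breast-Q.

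The cost is a change of wording in two places and one extra short questionnaire at a visit that already collects QOL, with a small added burden on patients.

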5.0 Randomization Factors

5.1 Assignment of treatments will be balanced with respect to the presence of immediate reconstruction (mastectomy/immediate reconstruction vs mastectomy/no immediate reconstruction) using a biased-coin minimization algorithm.[29]

6.0 Registration

- 4.1 Registration will entail confirming patient eligibility and signing the informed consent
- 4.2 Pretreatment tests/procedures (see section 4.0) will be completed within the guidelines specified on the assessment schedule.
- 4.3 All required baseline symptoms (see section 10.0) must be documented and graded.

7.0 Protocol Treatment

Doses throughout will be prescribed in Gy (RBE). One Gy will be the equivalent of one Gy (RBE) for proton therapy for the purposes of the descriptions below. Radiation therapy must begin within 12 weeks of the last breast cancer surgery or the last dose of adjuvant chemotherapy and no sooner than 14 days since the last chemotherapy. The dose, schedule, and timing (neoadjuvant vs adjuvant) of chemotherapy and endocrine therapy are at the discretion of the treating oncologists. Concurrent cytotoxic chemotherapy with radiotherapy is not allowed. Use of anti-HER2 therapy during radiotherapy is permitted.

7.1 Radiation Therapy Arm 1

Patients who are randomized to arm 1 will receive conventionally fractionated radiotherapy in daily fractions to the chest wall plus regional nodal area CTV (with setup uncertainty analyses of 3-5mm perturbations along each translation axis and 3% beam range uncertainty). Boosts to the chest wall after mastectomy are not permitted but nodal boosts to sites of initial gross disease are allowed.

7.2 Radiation Therapy Arm 2

Patients who had a lumpectomy or mastectomy and are randomized to arm 2 will receive hypofractionated radiotherapy in daily fractions to the chest wall plus regional nodal area CTV (with setup uncertainty analyses of 3-5mm perturbations along each translation axis and 3% beam range uncertainty). Boosts to the chest wall after mastectomy are not permitted but nodal boosts to sites of initial gross disease are allowed.

7.3 Dose Specifications

7.31 Arm 1 post-mastectomy plus regional nodal irradiation

7.311 Chest wall and regional nodes: 50 Gy (RBE) in 25 fractions of 2 Gy (RBE)

7.32 Arm 2 post-mastectomy plus regional nodal irradiation

7.321 Chest wall and regional nodes: 40.05 Gy (RBE) in 15 fractions of 2.67 Gy (RBE)

7.4 Treatment Technique

7.41 Radiation will be delivered using available scanning beam proton equipment at the treating institution.

7.5 Localization, Simulation, Immobilization

7.51 Simulation should be performed with the patient in the supine position

7.52 Patients should be optimally positioned with an immobilization device such as an alpha cradle cast, breast board or other customized immobilization device at the discretion of the treating physician.

7.53 Arm position may be up or down.

7.54 For patients who have an expander in place for reconstruction, the expander should be fully expanded or fully collapsed in order to optimize reproducibility. The expander should remain in the same condition from the time of CT simulation until the completion of radiotherapy.

7.55 The CT should extend cephalad to at least the level of the mandible to include both elbows and extend caudally to encompass the entire lung volume. The CT scan thickness should be $\leq 5\text{mm}$.

7.56 External skin markers, which may include permanent tattoos, are recommended for daily set-up.

7.57 KV image guidance will be performed daily. Other imaging modalities, such as CBCT and jVision RT, should be performed based on institutional guidelines.

7.58 Volumetric imaging may be performed with re-planning at the physician's discretion.

7.6 Treatment Planning

7.61 For proton planning, 1 en face or 2 oblique fields are generally recommended.

7.62 The use of skin bolus is not allowed

7.7 Target Volumes

The definitions for the CTV and normal structures for this protocol will generally follow the RTOG (Radiation Therapy Oncologic Group)-endorsed consensus guidelines for delineation for breast cancer [REDACTED] with exceptions described below.

7.71 Post-mastectomy chest wall and regional node target volumes (Arms 1 and 2)

Post-mastectomy chest wall and regional node CTV: Includes the chest wall, along with all 3 levels of the axilla, supraclavicular lymph nodes, and internal mammary lymph nodes. The chest wall contour is based on anatomical borders of the chest wall from the RTOG Breast Cancer Atlas but not extending deeper than the anterior surface of the ribs and intercostal muscles except in the vicinity of the internal mammary lymph nodes. The chest wall is also limited anteriorly to exclude the first 3 mm of tissue under the skin. In general, the chest wall CTV should include the mastectomy scar but not cross midline. Expanders, implants, or autologous tissue present for reconstruction is allowed and at least the most peripheral 1 cm should be included in the post-mastectomy chest wall and regional node CTV. In patients with subpectoral implants the implant may be excluded only with permission from the principal investigator or representative. The 3 levels of the axilla should generally follow the RTOG-endorsed consensus guidelines, although the superior border of level II of the axilla should extend to the most cranial CT-slice of the axillary vessels and [30] both the medial and lateral supraclavicular lymph nodes should

be included (Brown et al IJROBP 2015), as described by Dijkema and colleagues.[30] In addition, the internal mammary lymph nodes will be defined as the region of the internal mammary vessels plus an approximate 5 mm medial and 5 mm lateral margin, limited medially by the sternum and posteriorly by the lung and heart. The internal mammary lymph nodes should extend from the cranial CT-slice of the 4th rib to the cranial CT-slice of the jugulo-subclavian junction.[30]. The internal mammary lymph node structure should be incorporated into the CTV but it will also have its own separate individual constraints.

7.8 Critical Structures

- 7.81 Chest wall skin: Will be defined as the first 3 mm of tissue under the body surface anterior to the CTV and limited superiorly by the slice where the CTV is >5mm from the skin; this is generally at or below the inferior border of the clavicular head).
- 7.82 Supraclavicular skin (after lumpectomy or mastectomy): Will be defined as the first 3 mm of tissue under the body surface anterior to the Breast/chest wall CTV limited inferiorly by the last slice of “breast skin” and superiorly by the most superior slice of the CTV.
- 7.83 Heart: To be contoured on all cases. The contour should begin just inferior to the level in which the pulmonary trunk branches into the left and right pulmonary arteries (PA) and should extend to its most inferior extent near the diaphragm. The esophagus, ascending and descending aorta and inferior vena cava should be excluded from the heart contour. The pericardium should be included but not the anterior pericardial fat, if present.
- 7.84 Left anterior descending (LAD) interventricular branch: To be contoured on left sided cases. “Originates from the left coronary artery and runs in the interventricular groove between the right and left ventricles. If it is difficult to see, raising the level and lowering the window may help (e.g. level 50, window 150).”[31]
- 7.85 Right coronary artery (RCA). To be contoured on all right sided cases. “Originates from the right side of the ascending aorta. Due to the native heart position in the chest, on axilla CT, it appears to start inferior to the left coronary artery. It moves significantly with cardiac motion, so often the location can seem noncontiguous from axial CT slice to slice, as the position of the AV groove changes.”[31]
- 7.86 Ipsilateral lung: To be contoured on all cases, auto-segmentation with manual verification is permitted
- 7.87 Contralateral lung: To be contoured on all cases, auto-segmentation with manual verification is permitted

7.88 Total lung: To be contoured on all cases, auto-segmentation with manual verification is permitted

7.89 Esophagus: Should be contoured from its most superior extent at the lower border of the cricoid cartilage to the bifurcation of the trachea.

7.810 Internal mammary lymph nodes: Defined as the internal mammary vessels plus an approximate 3 mm medial and 3 mm lateral margin to include the adjacent soft tissues/fat pad, and limited medially by the sternum and posteriorly by the lung and heart. Should extend from the cranial CT-slice of the 4th rib to the cranial CT-slice of the jugulo-subclavian junction.[30]. Should be incorporated into the CTV but it will also have its own separate individual constraints.

7.811 Contralateral breast: Dose to the contralateral breast will not be constrained in treatment planning and therefore contouring of the contralateral breast is not required in this protocol. However, efforts should be made to limit inadvertent dosing of the contralateral breast.

7.812 Ipsilateral Brachial Plexus: Should be contoured when present in the CTV in addition to 3 slices above the CTV as described by Hall and colleagues.[32]

